	to 3000 mg/day, however, only a limited number of subjects have received GSK2816126.	clothing with long sleeves, sunglasses, and broad rim hat that protect the skin from sun exposure AND use a broad spectrum sunscreen (e.g., UVA and UVB protective with minimum SPF 30) on any uncovered areas of the body if outdoors from the time of first dose of study medication until at least 2 weeks (14 days) following last dose of study medication due to long elimination phase.
Hepatic Toxicity	
In first in human study EZH117208 (present study), an increase in level of ALT has been noted in the group of subjects receiving doses of 1800 mg to 3000 mg (single infusion dose). None of these ALT increases have been associated with increase in total bilirubin or INR and all have shown improvement following either withholding or discontinuing GSK2816126. The 3000 mg dose has been declared to exceed the MTD. The highest dose being explored in this study is 2400 mg .
 
In nonclinical species given GSK2816126, twice weekly for 2 and/or 4 weeks, changes in liver pathology (inflammation, hyperplasia) in dogs and clinical chemistry parameters (i.e. increases in ALT, AST, alkaline phosphatase (ALP), bilirubin and decreases in albumin) in rats and dogs were observed and were consistent with systemic inflammation. These effects were considered secondary to vascular damage at the infusion and/or surgical site and attributable to vascular or extravascular irritant (vesicant) effects of GSK2816126 and prolonged intravenous catheterization.
 
No current evidence suggests the presence of reactive metabolites. No glutathione conjugates were identified in the in vitro, ex vivo studies that were
	Dosing at 3000 mg has been discontinued, with the highest dose being explored is at 2400 mg. Continued laboratory and clinical monitoring for liver dysfunction (LFT, coagulation parameters INR/PTT, other blood chemistry, clinical observation for jaundice). Dose management and stopping criteria as per guidelines for non-hematologic toxicity (Section 3.8.3 and Table 4) and hepatic safety monitoring (Section 8.3.1)

Potential Risk of Clinical Significance	Data/Rationale for Risk	Mitigation Strategy

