ECG ^b	Pre-infusion and at the end of infusion except on Day 1 (Section 7.3.4). Two copies of the ECG tracing should be obtained at the time of the ECG, one to be kept in the study file for retrospective collection by the sponsor if necessary. ECG data should be reviewed by qualified personnel with experience in this study population	X	X ^b	X	X		On Day 4 of each cycle	X

	STUDY PHASE	SCREEN	First Treatment Period Cycle 1			Day 21	Continuation Phase Cycle 2 and beyond	Follow-Up^j
			Day 1 and 4^a	Day 8 and 11^a	Day 15 and 18^a			
	VISIT	Screen						
	VISIT WINDOW (\pmdays)	-14					$\pm 7^l$	$\pm 7^l$
Holter Monitoring	Continuous 12-lead Holter ECGs (obtained via a Holter monitor) will be acquired for a total of approximately 24 hours beginning an hour before infusion on Day 1 only		X (Day 1)					

	STUDY PHASE	SCREEN	First Treatment Period Cycle 1			Day 21	Continuation Phase Cycle 2 and beyond	Follow-Up^j
			Day 1 and 4^a	Day 8 and 11^a	Day 15 and 18^a			
	VISIT	Screen						
	VISIT WINDOW (\pmdays)	-14					$\pm 7^l$	$\pm 7^l$
ECHO /MUGA	At Screening	X						
Concomitant medications	See Section 9.2 for list of prohibited and cautionary medications	X	X	X	X	X	continuous	X
Adverse events (Refer to Section 8)	Adverse event assessment should be continuous	X	X	X	X	X	continuous	X
Blood Sampling: on dosing days, collect blood samples prior to dosing unless otherwise noted								
Chemistry	No need to repeat at pre-dose Day 1 if screening assessments were performed within 72 hours of first dose (- 1 day visit window after screening)	X	X	X	X	X	Prior to every infusion	X

	STUDY PHASE	SCREEN	First Treatment Period Cycle 1			Day 21	Continuation Phase Cycle 2 and beyond	Follow-Up^j
			Day 1 and 4^a	Day 8 and 11^a	Day 15 and 18^a			
	VISIT	Screen						
	VISIT WINDOW (\pmdays)	-14					$\pm 7^l$	$\pm 7^l$
Hematology	No need to repeat at pre-dose Day 1 if screening assessments were performed within 72 hours of first dose (- 1 day visit window after screening)	X	X	X	X	X	Prior to every infusion	X
Coagulation	PT/PTT/INR. No need to repeat at pre-dose Day 1 if screening assessments were performed within 72 hours of first dose (- 1 day visit window after screening)	X						

	STUDY PHASE	SCREEN	First Treatment Period Cycle 1			Day 21	Continuation Phase Cycle 2 and beyond	Follow-Up^j
			Day 1 and 4^a	Day 8 and 11^a	Day 15 and 18^a			
	VISIT	Screen						
	VISIT WINDOW (\pmdays)	-14					$\pm 7^l$	$\pm 7^l$

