- g. All events of possible study treatment-induced liver injury with hyperbilirubinemia defined as ALT ≥ 3 times ULN **and** bilirubin ≥ 2 times ULN ($>35\%$ direct) (or ALT ≥ 3 times ULN and INR >1.5 , if INR is measured) or termed 'Hy's Law' events (INR measurement is not required and the threshold value stated will not apply to subjects receiving anticoagulants).
 - **NOTE:** Bilirubin fractionation is performed if testing is available. If testing is not available, record presence of detectable urinary bilirubin on dipstick indicating direct bilirubin elevations and suggesting liver injury. If testing is unavailable and a subject meets the criterion of total bilirubin ≥ 2 times ULN, then the event is still reported as a SAE. If INR is obtained, include values on the SAE form. INR elevations >1.5 suggest severe liver injury.

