8.4.2. Prompt Reporting of SAEs and Other Events to GSK

SAEs, pregnancies, and liver function abnormalities and any other events meeting pre-defined criteria will be reported promptly by the investigator to GSK as described in the following table once the investigator determines the event meets the protocol definition for that event.

Type of Event	Initial Reports		Follow-up Information on a Previous Report	
	Time Frame	Documents	Time Frame	Documents
All SAEs	24 hours	SAE data collection tool	24 hours	Updated SAE data collection tool
“CV events” and/or “death”	Initial and follow up reports to be completed within one week of when the cardiovascular event or death is reported	“CV events” and/or “death” data collection tool(s) if applicable	Initial and follow up reports to be completed within one week of when the cardiovascular event or death is reported	Updated “CV events” and/or “death” data collection tool(s) if applicable
Pregnancy	2 Weeks	Pregnancy Notification Form	2 Weeks	Pregnancy Follow-up Form
Liver chemistry abnormalities (Section 8.3.1):				
ALT \geq 3 times ULN and bilirubin \geq 2 times ULN ($>35\%$ direct) (or ALT \geq 3 times ULN and INR >1.5 , if INR is measured) ^c	24 hours ^a	SAE data collection tool; Liver Event eCRF and liver imaging and/or biopsy eCRFs if applicable ^b	24 hours	Updated SAE data collection tool. Updated Liver Event eCRF ^b
ALT \geq 5 times ULN; ALT \geq 3 times ULN with hepatitis or rash or 3 times ULN \geq 4 weeks	24 hours ^a	Liver Event eCRF ^b	24 hours	Updated Liver Event eCRF ^b
ALT \geq 3 times ULN and <5 times ULN and bilirubin <2 times ULN	24 hours ^a	Liver Event eCRF does not need to be completed unless elevations persist for 4 weeks or subject cannot be monitored weekly for 4 weeks ^b		

- a. GSK to be notified at onset of liver chemistry elevations to discuss subject safety.
- b. Liver event documents should be completed as soon as possible
- c. INR measurement is not required; if measured, the threshold value stated will not apply to subjects receiving anticoagulants.

Methods for detecting, recording, evaluating, and following up on AEs and SAEs are provided in the SPM.

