9.2. Prohibited and Cautionary Medications

Subjects should not receive those medications listed as prohibited in Section [9.2](#)

Subjects should not receive other anti-cancer therapy including chemotherapy, radiation therapy, immunotherapy, biologic therapy, investigational therapy, hormone therapy (other than leuprolide or other GnRH agonists for mCRPC), surgery or tumour embolization while on treatment in this study. Other anti-cancer therapy should not be administered unless one of the following occurs: documented disease progression; unacceptable or unmanageable toxicity; subject is withdrawn from the study at the investigator's discretion or consent is withdrawn; or no further clinical benefit is anticipated which requires permanent discontinuation of study drug. .

Concurrent use of therapeutic warfarin may be allowed. However, increased monitoring of INR and bleeding with dose titration for warfarin is recommended due to potential increase in warfarin concentration when administered with study treatment GSK2816126. Anticoagulants that do not have reversal agents available are prohibited from 14 days prior to the first dose of study drug through completion of the Final Study Visit.

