15.3. Appendix 3: Liver Chemistry Monitoring, Interruption Stopping and Follow-up Criteria

15.3.1. Liver Safety Stopping Criteria and Required Action and Follow up Assessments

Phase I/II liver chemistry stopping and increased monitoring criteria have been designed to assure subject safety and evaluate liver event etiology (in alignment with the FDA premarketing clinical liver safety guidance).

<http://www.fda.gov/downloads/Drugs/GuidanceComplianceRegulatoryInformation/Guidances/UCM174090.pdf>.

Phase I/II liver chemistry stopping criteria and required follow up assessments

Liver Chemistry Stopping Criteria – Liver Stopping Event Subject with entry criteria $ALT \leq 2.5 \times ULN$	
ALT-absolute	$ALT \geq 5 \times ULN$
ALT Increase	$ALT \geq 3 \times ULN$ persists for ≥ 4 weeks
Bilirubin^{1, 2}	$ALT \geq 3 \times ULN$ and bilirubin $\geq 2 \times ULN$ ($>35\%$ direct bilirubin)
INR²	$ALT \geq 3 \times ULN$ and $INR > 1.5$, if INR measured
Cannot Monitor	$ALT \geq 3 \times ULN$ and cannot be monitored weekly for 4 weeks
Symptomatic³	$ALT \geq 3 \times ULN$ associated with symptoms (new or worsening) believed to be related to liver injury or hypersensitivity
Liver Chemistry Stopping Criteria – Liver Stopping Event Including subjects with documented liver metastases/tumor infiltration at baseline AND entry criteria $ALT > 2.5 \times ULN$ but $\leq 5 \times ULN$	
ALT-absolute	Both $ALT \geq 5 \times ULN$ and $\geq 2 \times$ baseline value
ALT Increase	Both $ALT \geq 3 \times ULN$ and $\geq 1.5 \times$ baseline value that persists for ≥ 4 weeks
Bilirubin^{1, 2}	$ALT \geq 3 \times ULN$ and bilirubin $\geq 2 \times ULN$ ($>35\%$ direct bilirubin)
INR²	$ALT \geq 3 \times ULN$ and $INR > 1.5$, if INR measured
Cannot Monitor	Both $ALT \geq 3 \times ULN$ and $\geq 1.5 \times$ baseline value that cannot be monitored for 4 weeks
Symptomatic³	Both $ALT \geq 3 \times ULN$ and $\geq 1.5 \times$ baseline value associated with symptoms (new or worsening) believed to be related to liver injury or hypersensitivity
Required Actions and Follow up Assessments following ANY Liver Stopping Event	

Actions	Follow Up Assessments

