
 • Immediately discontinue study treatment • Report the event to GSK within 24 hours • Complete the liver event eCRF and complete an SAE data collection tool if the event also meets the criteria for an SAE² • Perform liver event follow up assessments • Monitor the subject until liver chemistries resolve, stabilize, or return to within baseline (see MONITORING below) • Do not restart/rechallenge subject with study treatment unless allowed per protocol and GSK Medical Governance approval is granted (refer to Appendix 3) • If restart/rechallenge is not granted, permanently discontinue study treatment and may continue subject in the study for any protocol specified follow up assessments 	
 • Viral hepatitis serology⁴ • Blood sample for pharmacokinetic (PK) analysis, obtained approximately 48 h after last dose⁵ • Serum creatine phosphokinase (CPK) and lactate dehydrogenase (LDH). • Fractionate bilirubin, if total bilirubin\geq2xULN • Obtain complete blood count with differential to assess eosinophilia • Record the appearance or worsening of clinical symptoms of liver injury, or hypersensitivity, on the AE report form • Record use of concomitant medications on the concomitant medications report form including acetaminophen, herbal remedies, other over the counter medications • Record alcohol use on the liver event alcohol intake case report form

MONITORING:

For bilirubin or INR criteria:

- Repeat liver chemistries (include ALT, AST, alkaline phosphatase, bilirubin) and perform liver event follow up assessments within **24 hrs**
- Monitor subjects twice weekly until liver chemistries resolve, stabilize or return to within baseline
- A specialist or hepatology consultation is recommended

For All other criteria:

- Repeat liver chemistries (include ALT, AST, alkaline phosphatase, bilirubin) and perform liver event follow up assessments within **72 hrs**
- Monitor subjects weekly until liver chemistries resolve, stabilize or return to within baseline

For bilirubin or INR criteria:

- Anti-nuclear antibody, anti-smooth muscle antibody, Type 1 anti-liver kidney microsomal antibodies, and quantitative total immunoglobulin G (IgG or gamma globulins).
- Serum acetaminophen adduct high pressure liquid chromatography (HPLC) assay (quantifies potential acetaminophen contribution to liver injury in subjects with definite or likely acetaminophen use in the preceding week [[James, 2009](#)]).

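### Section 1.3.1 offers continued INR/PTT monitoring as mitigation for the ALT rises, but after the first dose no schedule or liver rule requires an INR

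*Protocol*

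**What the plan says.** The Hepatic Toxicity row of Section 1.3.1 reports ALT increases in subjects given 1800 to 3000 mg. It adds: "None of these ALT increases have been associated with increase in total bilirubin or INR". Dosing at 3000 mg has ended and 2400 mg is the highest dose still being explored. The mitigation column lists "Continued laboratory and clinical monitoring for liver dysfunction (LFT, coagulation parameters INR/PTT, other blood chemistry, clinical observation for jaundice" and refers to Section 3.8.3, Table 4 and Section 8.3.1.

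The coagulation row of Table 6 (Section 7.1) has a single mark, at screening. Its note reads "PT/PTT/INR. No need to repeat at pre-dose Day 1 if screening assessments were performed within 72 hours of first dose". Section 7.2 lists coagulation among the baseline tests, and Table 8 contains no coagulation test.

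The liver rules treat INR as optional:
- Section 8.2, item g: "INR measurement is not required and the threshold value stated will not apply to subjects receiving anticoagulants".
- Section 8.4.2, footnote c: "INR measurement is not required; if measured, the threshold value stated will not apply to subjects receiving anticoagulants".
- Appendix 3 (Section 15.3.1): the INR row of each stopping table carries the qualifier "if INR measured", and footnote 2 repeats that the test need not be done.
- Appendix 3, after a stopping event: "Repeat liver chemistries (include ALT, AST, alkaline phosphatase, bilirubin) and perform liver event follow up assessments within" 24 or 72 hours, depending on the criterion met. INR is not among the named tests or in the follow-up list.

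On-treatment INR is recommended in one place only. Section 9.2 says "increased monitoring of INR and bleeding with dose titration for warfarin is recommended", and the footnote to Table 12 repeats it.

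**The concern.** A site that follows Table 6 and Appendix 3 exactly will not carry out a safeguard that the risk section says is in place. The omission concerns a toxicity already observed in this study, within a dose range that is still partly open.

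INR also carries decision weight in this protocol. With ALT of at least 3×ULN, an INR above 1.5 stops treatment and makes the event an SAE, and Section 8.2 describes such a value as pointing to severe liver injury. Section 15.3.2 counts a raised INR in its definition of severe injury when listing risk factors for a fatal rechallenge. If nobody is obliged to measure INR, this limb depends on local habit. The only subjects for whom on-treatment INR is recommended are warfarin users, and the INR threshold does not apply to subjects on anticoagulants.

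**Working it through.** The protocol states no figure to reproduce. The check compares sections and then counts scheduled tests.

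**1. Scheduled tests after the first dose (Table 6)**

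| Test | Rest of Cycle 1 | Later cycles |
|---|---|---|
| Chemistry (includes ALT and bilirubin, Table 8) | Days 4, 8, 11, 15, 18, 21 = 6 draws | before every infusion |
| PT/PTT/INR | 0 | 0 |

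The conditional repeat in the coagulation note falls before the first dose on Day 1, so it adds nothing on treatment.

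**2. The affected subject**

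Take a subject not on anticoagulants with entry ALT ≤2.5×ULN. On treatment, ALT is ≥3 and <5×ULN, bilirubin is <2×ULN, there are no liver or hypersensitivity symptoms, and weekly visits are possible. Applying the Appendix 3 stopping rows in turn:
- ALT ≥5×ULN: not met.
- ALT ≥3×ULN persisting for at least 4 weeks: not met until the 4 weeks have passed.
- ALT ≥3×ULN with bilirubin ≥2×ULN: not met.
- ALT ≥3×ULN with INR >1.5: unknown unless someone orders the test.
- Cannot be monitored weekly: not met.
- Symptomatic: not met.

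The increased-monitoring table in Appendix 3 then lets this subject continue on weekly ALT, AST, alkaline phosphatase and bilirubin. If the rise is graded 2 and drug related, Table 4 allows a hold but equally allows unchanged dosing.

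**3. Exposure before the persistence rule stops treatment**

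4 weeks × 7 days = 28 days, the length of one cycle. Scheduled infusions in that span: 2 per week × 3 weeks = 6. Required INR measurements in that span: 0.

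**4. A secondary point on baseline INR**

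Entry (Section 5.2.1) allows PT/INR up to 1.5×ULN. The protocol gives no laboratory ULN for INR, so the values below are assumptions.

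| Assumed INR ULN | Highest entry INR = 1.5 × ULN |
|---|---|
| 1.0 | 1.50 |
| 1.1 | 1.65 |
| 1.2 | 1.80 |

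If the ULN exceeds 1.0, a subject may enter with INR above 1.5. That alone does not meet the stop, which also needs ALT ≥3×ULN. Once ALT reaches 3×ULN, however, the INR limb would be met with no change in INR at all.

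**The case against.** The strongest reply is that the operative liver rules agree with one another. Every one of them makes INR optional, and the protocol says the criteria were designed in line with regulatory liver-safety guidance. On that view the only flaw is a loose phrase in Section 1.3.1, which gives no frequency, and rewording it to testing as clinically indicated would end the contradiction. Section 7 lets the sponsor change the timing and number of safety assessments without an amendment. Appendix 3 requires the medical monitor to be told within 24 hours when ALT enters this band. Section 1.3.1 implies that some INR values were obtained in the subjects with ALT rises. Finally, a remedy triggered by ALT accepts event-driven testing, so a schedule with no routine INR is not by itself the defect.

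Much of this stands. Routine INR at every visit is not needed, the expected yield is low, and nothing prevents an investigator from ordering the test. What remains is that permission is not a requirement. The provisions in Section 7 and Appendix 3 make an INR possible, but neither asks for one. Rewording Section 1.3.1 alone would restore consistency by withdrawing a stated safety measure.

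A reader might infer three stronger points that the documents do not support:
- That subjects can enter already beyond the stopping threshold because of their INR. The stop is a joint ALT and INR criterion, and an entry INR above 1.5 alone does not meet it.
- That the absence of INR rises can no longer be confirmed in later subjects. It is not guaranteed, but unscheduled testing can still show it.
- That INR was deliberately excluded. The text makes it optional and states no such intent.

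**Conclusion.** The inconsistency is real and sits in the current text. Section 1.3.1 relies on continued INR/PTT monitoring, and nothing in the schedule or the liver rules requires it once dosing starts. The practical gap is one limb of the stopping and SAE rule, in a narrow group, for up to 4 weeks and 6 scheduled infusions. The ALT, bilirubin and symptom limbs still operate, with chemistry drawn before every later infusion. The protocol gives no frequency for this ALT band, so no number of affected subjects can be stated.

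The conclusion rests on reading the Table 6 coagulation row as a single screening mark, which its note and Section 7.2 support. Figures 1 and 2 of Section 8.3.1 are not shown, but Appendix 3 gives the same criteria in words, and its footnote 2 makes a contrary rule there unlikely. The change should be made because it concerns patient safety and costs little; no efficacy estimate depends on it.

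**What to change.** Require INR whenever on-treatment ALT is ≥3×ULN in subjects not on anticoagulants, on the same draw or at the latest before the next infusion, and again at each weekly check while ALT stays there. Testing on Day 1 of each cycle can remain optional. This needs four edits:
- add the conditional test to the coagulation row of Table 6;
- add INR to the Appendix 3 increased-monitoring actions and to the follow-up list after a stopping event;
- change the statements in Section 8.2, Section 8.4.2 and Appendix 3 footnote 2 that INR need not be measured, keeping the exemption for anticoagulant users;
- state how a subject with baseline INR above 1.5 is handled, for example by also requiring a rise from baseline before the INR limb counts.

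The cost is one extra assay on draws already taken, only in subjects with ALT ≥3×ULN, and possibly a few more treatment stops or SAE reports. If the sponsor prefers not to require INR, Section 1.3.1 should stop listing INR/PTT as continued monitoring, with the loss of that safeguard acknowledged.

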1.3.2. Benefit Assessment

Study EZH117208 is an open-label, dose escalation study and the first study of this agent to be conducted in humans. GSK2816126 has promising growth inhibitory activity in cell lines derived from multiple tumor types; however, it is unknown whether GSK2816126 will have efficacy in patients with these tumors. Thus, any potential beneficial effect for an individual subject attributable to GSK2816126 is unknown. Data obtained in Study EZH117208 may assist in progressing the knowledge base on lymphoma and other tumor types and their treatment(s), or help identify individuals more likely to benefit or have side-effects from GSK2816126. Study participants may benefit from the medical tests and screening performed during the study.

1.3.3. Overall Benefit: Risk Conclusion

Current data from GSK2816126 clinical study and nonclinical development indicate a potential for clinical utility in the treatment of subjects with relapsed and/or refractory DLBCL and/or transformed FL, NHL, multiple myeloma, and other solid tumors. Considering the overall poor outlook of these subjects on failing prior therapy and recognizing the measures taken to minimise risk to subjects participating in the Phase I clinical trials, the potential risks identified in association with GSK2816126 are justified by the anticipated benefits that may be afforded to subjects with the previously mentioned tumor types that have been shown in nonclinical models to respond to GSK2816126.

1.4. Communication Plan for Safety Evaluation

This phase I study is intended to enroll subjects at two or more sites. Safety evaluations will be closely monitored by a GlaxoSmithKline (GSK) Safety Review Team that includes the GSK medical monitor and GSK safety physician. There will be a 2 way communication between the local participating sites and the GSK team via email, fax and phone. The GSK team will review all safety data throughout the study, and safety findings with GSK2816126 will be discussed with investigators from all participating sites on a monthly basis and appropriate action will be taken. Urgent safety information will be shared with all the participating sites at the earliest possible time after the data becomes available, or sooner if necessary.

